Based on established literature, we hypothesized that a duration of 24 weeks employing the BSE will yield positive impact on user biomechanics characterized by diminished back muscle activity and decreased knee flexion indicating a more stoop lifting technique (Diamond-Ouellette et al., 2022; Poggensee & Collins, 2021; Schröder Jakobsen et al., 2024). Furthermore, we hypothesized that prolonged utilization of the BSE will increase exoskeleton comfort and acceptance among users, concomitant with a reduction in perceived work intensity and occurrences of musculoskeletal discomfort, due to the anticipated mitigation of biomechanical load (Kazerooni et al., 2019; Schröder Jakobsen et al., 2024).

Section 3: Trial methods

Trial design

Item 9: Description of trial design

This trial was designed as a randomized controlled parallel intervention trial. Exoskeleton usage was allocated to the participating workers in a 1:1 ratio. The workers were randomized to intervention and controls. The intervention group was allocated a BSE for a 24-week period to perform their work tasks, while the control group performed their work tasks as normal for the same period. The primary endpoint was at the 24-week post-test.

Randomization

Item 10: Randomization details

The randomization was performed by an external blinded researcher not involved in data collection or assessments. After informed consent and baseline assessments had been conducted, the participants were randomly assigned to either intervention or control group using stratified randomization. Sex, work experience, and previous experience issues of low back-pain were used as strata.

Sample size

Item 11: Full details of sample size calculations

A priori sample size calculation for a repeated measure, within-between interaction design was conducted to estimate the required sample size to achieve a power of 80%. The calculation was based on effect sizes previously reported on training effects of the present BSE on muscular activity from SEMG erector spinae measurements ($\eta^2 \geq .370$) (Schröder Jakobsen et al., 2024). A two-sided significance level at .05 was set and revealed that a total minimum of 18 workers was required resulting in an actual power of .838. To account for a 10% drop-out, a total of 20 workers (10 per group) were enrolled.

Framework

Item 12: Description and hypothesis testing framework

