Primary outcomes (biomechanical measurements) were evaluated in a within-between interaction framework, hypothesizing that the workers would experience a reduction in muscular activity and changed kinematics when using the BSE, and further that the reduction will increase from baseline to post-test in line with previously reported training effects (Diamond-Ouellette et al., 2022; Poggensee & Collins, 2021;

Schröder Jakobsen et al., 2024). Secondary outcomes, were evaluated in a superiority framework, hypothesizing that workers using the BSE would witness a reduction in musculoskeletal discomfort and perceived work intensity, and increased acceptance of comfort in relation to BSE usage. A significance level of .05 will set.

Statistical interim analysis and stopping guidance

Item 13:

No interim analysis was planned, and no adjustment of significance level was made. No stopping rules was defined a priory.

Timing of final analysis

Item 14:

The analysis of primary, secondary, and other outcomes was conducted collectively when all workers had completed the test session post the 24-week intervention/control period. The 24-week intervention was expected to finish in April 2024. Biomechanical data from baseline and post-test, and questionnaire data from all the data points (baseline + 4-, 8-, 12-, 16-, 20-weeks, and post-test) were be included in the analysis.

The analysis of the primary, pre-specified secondary, and other outcomes (item 26) will be reported in the primary publication. The remaining outcomes will be reported in the secondary publication.

Timing of outcome assessment

Item 15:

Biomechanical outcomes (surface electromyography (SEMG) and kinematics) and perceived effort will be evaluated at baseline and post-tests. The questionnaire assessed outcomes (perceived work intensity, exoskeleton comfort and acceptance, and musculoskeletal pain) will be evaluated continuously during the intervention period at four-week intervals ending at post-test. Further details can be found at the published study protocol (NCT05890300).

Section 4: Statistical principles

Confidence intervals and p-values

Item 16: Level of statistical significance

All conducted statistical tests will be two-sided and evaluated by a significance level of 5% (i.e., $p = .05$).

Item 17: Description of planned adjustment for multiplicity

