To take precaution for multiplicity, multivariate statistical tests will be conducted to reduce the number of analyses ran, and thus the family-wise error rate. Additionally, Bonferroni corrections will be conducted to reveal significant differences when more repeated measures are occurring, which is considered a conservative approach in terms of reducing family-wise errors (Robert, 2020).

Item 18: Confidence intervals

The presented confidence intervals will be 95% and be two-sided.

Adherence and protocol deviation

Item 19a: Definition of adherence to interventions

Adherence will be defined as the workers of the intervention group compliance to BSE usage during the 24-week period. The protocol consists of a 5-weeks familiarization period consisting of progressive usage of the BSE (Schröder Jakobsen et al., 2023), followed by 19 weeks of minimum 18-hours of BSE usage per week. Adherence is self-registered day-by-day by the individual worker and monitored by the principal researcher.

Item 19b: Description of how adherence to intervention will be presented

Adherence to the intervention will be reported as weekly reported hours of BSE usage during the full 24-week period. Weekly hours of BSE usage will be reported at both individual and group level.

Item 19c & 19d: Definition of protocol violation for the trial and how they will be presented

It is specified as an exclusion criterion if workers resigns / get laid off during the intervention period.

Analysis populations

Item 20: Definition of analysis populations

The analysed population corresponded to the workforce of a specific department at a Danish logistics company. The department consists of a total workforce of approx. 70 fulltime employees. Only fulltime workers were included in the trial. Workers who should resign during the intervention period will be excluded from the analysis.

Section 5: Trial population

Screening data

Item 21: Reporting of screening data

The recruitment period will be showcased from start to end alongside the total number of workers screened for eligibility.

Eligibility

Item 22: Summary of eligibility criteria

Workers were eligible to participate in the trial if they fulfilled the inclusion criteria:

- Full-time employed at the department handling fruits and vegetables at Dagrofa Logistics A/S
- No major injuries affecting their daily work tasks
- No plans of retiring before the end of the intervention period

Study exclusion criteria were:

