The remaining secondary outcomes will be assessed for normality and sphericity using an approach similar to the primary outcomes. However, a different statistical analysis will be conducted due to the difference in factors. A one-way repeated measures multivariate analysis of variance (1RM-MANOVA) with timepoints (baseline, 4-, 8-, 12-, 16-, 20-weeks, and post-test) as the independent factor and comfort, performance,

liking, work intensity, and musculoskeletal discomfort as dependent outcomes will be used for assessment. If any significant change is detected, an additional post hoc (Bonferroni) analysis will be performed.

The primary outcomes (including perceived effort) will be reported in figures including with /without BSE usage measures from baseline and post-test. In this case mean and individual values from both groups will be reported. The remaining secondary outcomes will be reported in figures including data from all time points (baseline, 4-, 8-, 12-, 16-, 20-weeks, and post-test). Similarly, mean, and individual values from both groups will be reported.

The individual BSE usage will be depicted in a graph for the workers included in the intervention group. This will include week-to-week reporting of individual BSE usage and group mean. The BSE usage will not be statistically analysed.

The secondary publication will focus on the potential changes in productivity of the worker when using the BSE. It will include a regression analysis between individual productivity of the worker, and the hours using the BSE. Additional outcomes will also be included in the publication, i.e., monitoring of temporal changes in musculoskeletal discomfort during the intervention period. The coherence between productivity and BSE usage will be depicted in scatter plots.

Missing data:

Item 28: Reporting and assumptions/statistical methods to handle missing data (e.g., multiple imputation)

If any worker was excluded from the trial initial to the post-test (i.e., due to resignation), none of the excluded worker's data will be included in the analysis. Number of data points available in each group at any timepoint will be displayed in the primary publication. Workers violating the protocol by using the BSE less than intended, will not be excluded from the analysis. However, the effect of this potential issue will be handled in additional analyses (see below).

Additional analyses

Item 29:

The following additional analyses may be added:

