- Correlations between demographics and BSE usage to analyse the potential effects of demographics on exoskeleton acceptance.
- Cluster analysis of the effect of BSE usage on primary outcomes to analyse potential differences between workers in the intervention group with high and low adherence to BSE usage.

Harms

Item 30: Sufficient detail provided on summarizing harms

This study is designed to identify any harms or adverse events that may occur during the intervention. Self-reported changes in musculoskeletal discomfort and perceived work intensity will be monitored during the trial (see table 2). Additionally, the workers will at each timepoint be able to pass their individual feedback on the BSE, in term of what they 'least like', 'most like', and if they would change anything about the exoskeleton, in an open-ended questionnaire. Adverse events will be descriptively summarized for both groups and reported in the primary publication.

Statistical Software

Item 31: Details of statistical package used for the analysis

The statistical package IBM Corp. 2022. IBM SPSS Statistics for windows, Version 27.0. Armonk, NY: IBM Corp. was used for data management and analysis.

References

Item 32: Data Management

All the data will be stored in accordance with the Danish Personal Data Protection Act and other relevant Danish legislation. Biomechanical data is recorded in the original software file format (Noraxon and mvnx, respectively) and later exported to Matlab (MAT) format. Questionnaire data is recorded in hard copy during the outcome assessments and later noted in Excel spreadsheets. The main data set will not contain any personal information. Additionally, no personal information of the participants will be shared by the principal investigator and will be stored securely for his eyes only.

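### Workers who resign or are laid off after randomisation lose all their data, so the questionnaire outcomes become a stayers-only analysis

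*SAP*

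**What the plan says.** Three items of the SAP combine into one rule.

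- Item 19c/d: "It is specified as an exclusion criterion if workers resigns / get laid off during the intervention period".
- Item 20 (analysis populations): "Workers who should resign during the intervention period will be excluded from the analysis". This item names resignation only; lay-off comes in through Item 19c/d.
- Item 28 (missing data): for a worker excluded before the post-test, "none of the excluded worker's data will be included in the analysis".

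Item 10 fixes the order of events: "After informed consent and baseline assessments had been conducted, the participants were randomly assigned to either intervention or control group". Anyone who leaves during the 24 weeks has therefore already been randomised.

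Three other statements bear on the point. Item 28 keeps low users of the exoskeleton (BSE): "Workers violating the protocol by using the BSE less than intended, will not be excluded from the analysis". It also promises counts: "Number of data points available in each group at any timepoint will be displayed in the primary publication". Item 30 (harms) names self-reported discomfort and work intensity as what is monitored, and adds: "Adverse events will be descriptively summarized for both groups and reported in the primary publication".

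The SAP defines no all-randomised set. It gives no available-data analysis or imputation, and no sensitivity analysis for leavers.

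**The concern.** Leaving the job happens after allocation and need not be unrelated to the outcomes. The SAP's introduction describes the work as strenuous and linked to musculoskeletal disorders. Discomfort, workload or dislike of the device could each contribute to a worker leaving, and the questionnaires measure closely related things. Removing leavers entirely means that the groups analysed are no longer the groups randomised.

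Item 28 also treats two similar events differently. A worker who stops using the BSE but stays employed is analysed as allocated, while one who leaves is erased, including visits completed before leaving.

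At stake are the secondary conclusions on discomfort, work intensity and comfort, and the completeness of the harms account. With ten workers per arm, each worker is 10% of an arm.

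**Working it through.** **The plan's own figures.** Item 11 gives a minimum of 18 workers, power .838, and 20 enrolled to allow for 10% drop-out.

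- Drop-out allowance: 18 / (1 − 0.10) = 20, as stated.
- Power: .838 is reproduced for a 2-group, 2-measurement interaction if .370 is entered as Cohen's f with an assumed correlation of 0.5. Then λ = f² × N × m / (1 − ρ) = 0.1369 × 18 × 2 / 0.5 = 9.86 on 1 and 16 df, and power is .838. On the same basis it is .879 at N = 20 and .786 at N = 16.

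The allowance therefore protects precision if no more than two workers leave. It does nothing about which workers leave.

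**Data discarded.** Item 14 and Table 2 schedule questionnaires at baseline, weeks 4, 8, 12, 16 and 20, and post-test, seven per worker.

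- Scheduled in total: 20 × 7 = 140.
- Most that one leaver can have completed: 6 (baseline to week 20).
- Two leavers, the planned 10%: up to 2 × 6 = 12, and 12 / 140 = 8.6%. This maximum needs both to leave after week 20.

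**What is avoidable, by outcome.**

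| Outcome | Assessed | Effect of the rule |
|---|---|---|
| SEMG, kinematics, perceived effort | Baseline, post-test | Small: a leaver has no post-test under any rule |
| Discomfort, work intensity, comfort | Seven visits | Up to six usable visits per leaver deleted |

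**Possible shift in an arm mean (assumed inputs).** The SAP gives no figure for how leavers differ from stayers. Let d of n = 10 workers in an arm leave, with leavers g SD away from stayers. The full-arm mean differs from the stayers' mean by d × g / n.

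- d = 1: g = 0.5 gives 0.05 SD; g = 1.5 gives 0.15 SD.
- d = 2: g = 0.5 gives 2 × 0.5 / 10 = 0.10 SD; g = 1.5 gives 2 × 1.5 / 10 = 0.30 SD.

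**How often the rule would bite.** If each worker leaves independently with probability 0.10, the chance that at least one of ten in a given arm leaves is 1 − 0.9¹⁰ = 0.65.

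**Where the two leavers fall.** With two leavers among 20 and no effect of arm on leaving, both are in the BSE arm with probability (10 × 9) / (20 × 19) = 0.24. One leaver per arm with equal gaps gives no net shift between arms.

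**Harms.** Item 28 removes a leaver's data from the analysis. Item 30 promises a summary for both groups without saying whether leavers are counted. Read together, the two items leave this open.

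**The case against.** The case for leaving the rule alone has real content.

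- **Primary endpoint.** Biomechanics and perceived effort need a post-test, so those analyses would rest on much the same workers under any rule. This stands, and it limits the point to the questionnaires and harms.
- **Direction.** A reader might infer that the rule flatters the BSE. The SAP does not support that. Back trouble and workload can drive controls out too, Item 8 expects the BSE to reduce load, and lay-off is the employer's decision. If overloaded controls leave, deletion works against the BSE.
- **Who is deleted.** A reader might also infer that the rule removes just the workers for whom the device failed. The trigger is leaving employment. Someone who rejects the BSE and stays is kept, and someone who leaves for an unrelated reason is deleted.
- **Size.** A shift in raw points cannot be given for discomfort, since the SAP states no 0–10 range for the Cornell questionnaire. Item 27 gives time point as the only factor in the questionnaire analysis, so a gap that was constant from baseline would not bias change over time. The SD range above describes an arm mean at a visit and is no prediction of the trial's error.
- **Transparency.** Counts per group and time point, and the exclusions and withdrawals in the flow diagram (Items 23 and 24), make losses visible. They do not correct selection, and the flow-diagram list does not call for reasons. The blinded interpretation in Item 32 comes after the deletion.

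What remains is that data in hand are thrown away on a post-randomisation criterion that may be related to the outcomes.

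**Conclusion.** The point holds for the secondary questionnaire outcomes. The SAP fixes a rule that discards every observation from workers who leave after randomisation, up to 12 of 140 scheduled questionnaires at the planned drop-out. The result is a stayers-only analysis open to selection bias of unknown direction and size. The figure of 0.10 to 0.30 SD for an arm mean rests on two assumptions: two leavers in one arm, and a leaver–stayer gap of 0.5 to 1.5 SD. If nobody leaves, the rule does no harm; the SAP does not say whether anyone did.

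The primary biomechanical result is little affected. It would also go too far to say that the plan drops leavers' adverse events. Item 30 does not say so, and the defect there is an ambiguity with Item 28 that needs to be reconciled.

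**What to change.** 1. Define the analysis set in Item 20 as all randomised workers in their allocated arm, and remove the leaver exclusion from Items 19c/d, 20 and 28.
2. Analyse the scored questionnaire outcomes with a likelihood-based mixed model using every completed visit. Removing the exclusion is not enough by itself, because a repeated-measures MANOVA needs a complete set of visits from each worker. The open-ended liking questions are outside this model.
3. Keep the completer analysis as a sensitivity analysis.
4. For biomechanics and perceived effort, use workers with a post-test and report leavers by arm and reason.
5. State in Item 30 that adverse events and discomfort are summarised for all randomised workers, and word Item 28 to agree.

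Cost: no extra visits. The 1RM-MANOVA is replaced for the scored questionnaires, which is a little more analysis work, and reasons for leaving must be recorded. The mixed model still assumes data missing at random, so it reduces the selection problem without removing it.
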